4.4 Treatment of Subjects

Once enrolled in the study, the PI or the PI's assistant will administer the assigned treatment on a daily basis at the hospital site.

4.5 Medication

Proxalutamide showed no significant inhibition on CYP1A2 and CYP2E1, weak inhibition on CYP2D6, CYP2C9, CYP2C19 and CYP3A (midazolam), but obvious inhibition on CYP3A4 (testosterone). Potential inducer on CYP3A4 at a concentration of 10 μ M. No inductive effects on CYP1A2 and CYP2B6 were observed in the level of enzymatic activity. Co-administration of strong/moderate CYP3A4 inducer, strong/moderate CYP3A4 inhibitor, sensitive CYP3A4/ CYP2D6 substrates and narrow therapeutic index with Proxalutamide should be used cautiously (See Appendix 1).

Note: No interaction has been reported between Proxalutamide, Nitazoxanide, and azithromycin.

Therapy prior to enrollment with any other treatment for COVID-19 or the SARS-CoV-2 infection are permitted but must be discontinued on enrollment. There is no waiting period between discontinuation of these treatments and administration of the study intervention; however, these prior treatments and their end date should be documented in the Concomitant Medication CRF.

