3.2 Study Design/Type

This study is designed as a prospective, interventional, placebo controlled, double-blinded, randomized parallel assignment study. The study will have 2 arms:

Arm 1: Subjects administered Nitazoxanide 500 mg b.i.d for 5 days + azithromycin 500mg q.d for 5 days + Proxalutamide 300mg q.d for 14 days

Arm 2: Subjects administered Nitazoxanide 500 mg b.i.d for 5 days + azithromycin 500mg q.d for 5 days + Proxalutamide placebo 300mg q.d for 14 days

Study Environment:

This is a multi-center study to be conducted at multiple hospitals (the sites). This exact protocol will be followed during the study. There will be one or more PIs. The study will be approved by the appropriate Ethics Committees (IRBs). Data collection will be performed at each site by study personnel under the supervision of the PI.

Study Design:Phase I: Enrollment (within 24 hours of admission to hospital):

1. Each subject will be evaluated for the inclusion and exclusion criteria
2. Each subject will undergo a physical examination
3. Each subject (or legally authorized representative) will complete and sign the Informed Consent Form
4. Each subject will be assigned a subject study number
5. Each subject will be randomly assigned to an Arm (Section 3.3)
6. Based on the Arm assignment, each subject will be administered the intervention
7. All information will be recorded in the appropriate CRFs

Phase II: Outcome Assessment at Site (days 1-14):

1. Each subject will be evaluated daily by the PI for the outcomes of this study
2. Based on the Arm assignment, each subject will be administered the intervention
3. The PI will assess each subject for any treatment related adverse events
4. All information will be recorded in the appropriate CRFs

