4.5 Medication

Proxalutamide showed no significant inhibition on CYP1A2 and CYP2E1, weak inhibition on CYP2D6, CYP2C9, CYP2C19 and CYP3A (midazolam), but obvious inhibition on CYP3A4 (testosterone). Potential inducer on CYP3A4 at a concentration of 10 μ M. No inductive effects on CYP1A2 and CYP2B6 were observed in the level of enzymatic activity. Co-administration of strong/moderate CYP3A4 inducer, strong/moderate CYP3A4 inhibitor, sensitive CYP3A4/ CYP2D6 substrates and narrow therapeutic index with Proxalutamide should be used cautiously (See Appendix 1).

Note: No interaction has been reported between Proxalutamide, Nitazoxanide, and azithromycin.

Therapy prior to enrollment with any other treatment for COVID-19 or the SARS-CoV-2 infection are permitted but must be discontinued on enrollment. There is no waiting period between discontinuation of these treatments and administration of the study intervention; however, these prior treatments and their end date should be documented in the Concomitant Medication CRF.

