3.2 Study Design/Type

This study is designed as a prospective, interventional, placebo controlled, double-blinded, randomized parallel assignment study. The study will have 2 cohorts: men and women and 2 arms:

Arm 1: Subjects administered Proxalutamide 300mg q.d for 14 days + standard of care as determined by the PI at the site

Arm 2: Subjects administered Proxalutamide placebo 300mg q.d for 14 days + standard of care as determined by the PI at the site

Study Environment:

This is a multi-center study to be conducted at multiple hospitals (the sites). This exact protocol will be followed during the study. There will be one or more PIs. The study will be approved by the appropriate Ethics Committees (IRBs). Data collection will be performed at each site by study personnel under the supervision of the PI.

Study Design:

Phase I: Enrollment (within 5 days of admission to hospital):

1. Each subject will be evaluated for the inclusion and exclusion criteria

2. Each subject will undergo a physical examination
3. Each subject (or legally authorized representative) will complete and sign the Informed Consent Form
4. Each subject will be assigned a subject study number
5. Each subject will be randomly assigned to an Arm (Section 3.3)
6. Based on the Arm assignment, each subject will be administered the intervention
7. All information will be recorded in the appropriate CRFs

Phase II: Outcome Assessment at Site (days 1-28):

1. Each subject will be evaluated daily by the PI for the outcomes of this study
2. Based on the Arm assignment, each subject will be administered the intervention
3. The PI will assess each subject for any treatment related adverse events
4. All information will be recorded in the appropriate CRFs

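### Section 4.5 tells sites to stop other COVID-19 treatment at enrolment without exempting the standard of care that both arms are assigned, and expressly requires only prior treatments to be recorded

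*Combined protocol and SAP*

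**What the plan says.** The combined document holds two protocol versions: a male-only one and the current one, which adds a female cohort. The current text governs.

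- Stop rule (current 4.5, Medication): "Therapy prior to enrollment with any other treatment for COVID-19 or the SARS-CoV-2 infection are permitted but must be discontinued on enrollment".
- Treatment arms (current 3.2, repeated in 3.3): Arm 1 is "Proxalutamide 300mg q.d for 14 days + standard of care as determined by the PI at the site". Arm 2 is the same with placebo.
- Enrolment window (current 3.2): "Enrollment (within 5 days of admission to hospital").
- Recording (current 4.5): "these prior treatments and their end date should be documented in the Concomitant Medication CRF".
- A note kept in the current 4.5: "No interaction has been reported between Proxalutamide, Nitazoxanide, and azithromycin".

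In the male-only version, Arm 1 was "Nitazoxanide 500 mg b.i.d for 5 days + azithromycin 500mg q.d for 5 days + Proxalutamide 300mg q.d for 14 days", with the same two background drugs in Arm 2. Enrolment was "Enrollment (within 24 hours of admission to hospital"), and 4.5 already said that prior COVID-19 treatments "are permitted but must be discontinued on enrollment".

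No section of the current protocol lists what standard of care may contain or which COVID-19 drugs may continue or start after enrolment. The final statistical plan does not mention background therapy.

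**The concern.** The stop rule and the arm definition give a site two different instructions for the same patient. Someone admitted four days ago and already on COVID-19 treatment may have it withdrawn at one hospital and continued at another, with each site believing it is following the protocol. Section 3.2 asks for exact adherence, and section 1.3 bars deviations without ethics approval except to remove an immediate hazard. Neither says which of the two sections prevails.

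Three things are at stake. A patient with active disease could lose treatment the investigator considers standard. Care could differ between sites for reasons of wording rather than medicine. And the 14-day recovery ratio and 28-day mortality will naturally be read as the effect of proxalutamide added to standard care, while the data expressly required do not show what that care was.

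**Working it through.** The documents do not give the share of patients on treatment at enrolment, or any effect of proxalutamide by type of background care. The check is therefore a comparison of texts, not a calculation.

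1. **What does the word *other* refer to?** In the male-only version both arms had a closed background of nitazoxanide plus azithromycin, so *other treatment* meant anything except those drugs and the study drug. The rule was coherent. In the current version the background is open, but the stop sentence is unchanged and so is the nitazoxanide/azithromycin note. The change of background is not itself an error. It explains why the sentence no longer fits.

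2. **Literal reading.** Every COVID-19 treatment begun before enrolment stops, including what the site regards as standard. Section 4.5 does not forbid starting standard of care afterwards, so a site might stop a drug and restart it, or stop it for good. The text does not say which.

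3. **Reconciling reading.** *Other* means other than the assigned arm. Standard of care is then exempt, and the rule reaches only drugs outside it. This is workable, but the boundary is whatever each investigator regards as standard, and no section requires a site to write that down.

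4. **How many patients could be affected?** The share is unknown, but the opportunity has grown. The enrolment window went from 24 hours to 5 days after admission. Eligibility (section 4.1) went from ordinal scores 3, 4 or 5 to scores 3 to 6, which adds patients on non-invasive ventilation or high-flow oxygen. More patients, and sicker ones, can already be on treatment when the rule applies.

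5. **What do the express recording duties capture?**
   - Treated before enrolment and stopped: drug and end date required.
   - Treated before enrolment and continued: no clear duty, because the instruction assumes treatment has ended.
   - Treatment started after enrolment: no express duty.
   - Never treated: nothing to record.

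   The last three groups cannot be reliably told apart from what the protocol expressly requires. Section 3.4 lists medical history and efficacy parameters. Section 11 adds demographics, adverse events and a general reference to study-related information. Both then state that no further data are recorded. On-study use of Appendix 1 drugs, for which 4.5 asks caution, has no express recording duty either.

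6. **Does the rule act differently by arm?** No. It applies at enrolment to everyone, under blinded 1:1 allocation. It does not itself create a difference between arms.

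**The case against.** The strongest reply is that there is no real contradiction. Section 4.5 concerns prior therapy with other treatments, and standard of care belongs to the assigned arm, so the natural reading exempts it. A site that stopped everything would still owe the patient standard of care under 3.2. On that view, a population whose standard treatment was withdrawn is an inference, not something the plan intends. It may well be the intended reading. But the text does not say so, and a literal reader would reach the opposite conclusion.

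It can also be said that the recording gap rests partly on a form the documents do not show. A Concomitant Medication CRF exists, section 3.2 says in general terms that information goes into the CRFs, and the charts remain available. That stands: the form may capture more than the protocol requires. The supportable point is that no express duty is written.

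A reader might infer three stronger points that the documents do not support:

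- *The comparator is undefined.* Placebo once daily for 14 days plus site-chosen care is an ordinary pragmatic comparator. What is unclear is whether treatment already running belongs to that care.
- *The pooled result loses power because it mixes two questions.* Any such figure needs an assumed difference in effect between stopped and continued treatment, for which the documents give no basis. Any add-on trial could face such a difference even with clear wording.
- *Stopping or continuing treatment is confounded with arm at some sites.* The final statistical plan says randomisation was changed at a small remote hospital, but it gives no unequal allocation ratio and adds a hospital-site subgroup analysis in response. Any resulting confounding would exist even with a perfect 4.5, so it is a separate matter.

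**Conclusion.** The point holds as a defect of instruction and recording. The current stop rule has no standard-of-care exemption, conflicts on its face with the arm definition, and is paired with a recording duty that expressly covers only prior treatments. It should be corrected because it touches the care of hospitalised patients, and because a claim of benefit on top of standard care needs a description of that care.

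Its size cannot be expressed as lost power or inflated type I error, and the randomised test is not directly biased by it. How far care actually diverged depends on how sites read 4.5 and on what the CRF collected, neither of which the documents show. If every site took the reconciling reading and the form captured all co-medication, the practical harm would be small and a wording correction would suffice.

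**What to change.** 1. Replace the stop sentence in 4.5 with: *Standard of care for COVID-19 chosen by the PI may continue or start after enrolment in both arms; COVID-19 treatments outside the site's standard of care must stop before the first dose.*
2. Require every COVID-19 drug and every Appendix 1 drug given from Day 1 to Day 28 on the Concomitant Medication CRF, with drug, dose, start and stop. For patients already treated, take this from the charts.
3. Report co-treatment descriptively by arm and by site next to the efficacy results.

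The primary test should stay as it is with respect to background treatment. Stopped or continued status may be settled after randomisation, so stratifying on it could introduce bias. A rule letting a stratified result override the unadjusted one would in effect replace the primary analysis.

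The cost is a rewritten sentence, one CRF page, and chart abstraction for patients already enrolled, up to about 600 if all are. No extra patients and no endpoint change are needed. The final statistical plan states that its changes were made during manuscript writing. For patients who had finished treatment by then, only the chart abstraction and descriptive reporting can still help; the wording change serves any further enrolment.

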4.6 Monitoring for subject compliance

The PI will monitor each subject's chart to assure daily administration of the treatment by the study staff.

5 Assessment of Efficacy

5.1 Efficacy Parameters

The following efficacy parameters will be assessed and recorded in the CRF.

I. COVID-19 Ordinal Scale:

The ordinal scale is an assessment of the clinical status of each subject. The scale is defined as follows:

- 8. Death;
- 7. Hospitalized, on invasive mechanical ventilation or ECMO;
- 6. Hospitalized, on non-invasive ventilation or high flow oxygen devices;
- 5. Hospitalized, requiring supplemental oxygen;

4. Hospitalized, not requiring supplemental oxygen- requiring ongoing medical care (COVID-19 related or otherwise);
3. Hospitalized, not requiring supplemental oxygen - no longer requires ongoing medical care;
2. Not hospitalized, limitation on activities;
1. Not hospitalized, no limitations on activities

II. Time to Recovery:

Time to recovery is defined as the first day on which the subject satisfies one of the following three categories from the ordinal scale (defined in Section 5.1): 3)

Hospitalized, not requiring supplemental oxygen - no longer requires ongoing medical care; 2) Not hospitalized, limitation on activities and/or requiring home oxygen; or 1) Not hospitalized, no limitations on activities.

III. “Multiple Combined Sensitive Outcome Detect Method” (combining items I and II):

1. (WHO COVID ORDINAL OUTCOMES SCALE):
 - a. 1 dia; b. 2 dias; c. 3 dias; d. 7 dias; e. 14 dias; f. 21 dias; g. 30 dias (cuja escala é plenamente contemplada por alguns dos desfechos descritos abaixo)
2. TEMPO ATÉ RECUPERAÇÃO – regressão aos níveis 1 e 2 da WHO COVID Ordinal Outcomes Scale (dias)
3. POSITIVIDADE DA rtPCR-SARS-CoV-2 a. 7 dias; b. 14 dias; c. 30 dias (%)
4. TEMPO ATÉ REMISSÃO DE CADA SINTOMA (dias)
5. TEMPO ATÉ REMISSÃO COMPLETA DOS SINTOMAS (dias)
6. TEMPO ATÉ RECUPERAÇÃO DA CAPACIDADE DE REALIZAÇÃO DE ATIVIDADES DIÁRIAS DEVIDO AOS SINTOMAS DE COVID-19 (Nível 1 da WHO COVID Ordinal Outcomes Scale) (dias)
7. NECESSIDADE DE UNIDADE INTENSIVA (%)
8. NECESSIDADE DE VENTILAÇÃO MECÂNICA (%)
9. TEMPO DE HOSPITALIZAÇÃO (dias)
10. TEMPO DE OXIGENIOTERAPIA (dias) (se necessário)
11. TEMPO DE UNIDADE DE TERAPIA INTENSIVA (dias) (se necessário)
12. TEMPO DE VENTILAÇÃO MECÂNICA (dias) (se necessário)
13. NECESSIDADE DE USO DE VASOATIVOS (%)
14. MORTE (%)

5.2 Method and Timing

For each study day while the subject is hospitalized, the PI will record the clinical assessment on an 8- point ordinal scale as follows:

- Day 1 – The clinical assessment at the time of enrollment.

- Day 2 - The most severe clinical assessment occurring any time between enrollment and midnight the day following enrollment.
- Day 3-28 (or until discharged) - The most severe assessment occurring from midnight to midnight of the prior day (e.g., the value recorded on Day 3 will be the most severe outcome that occurred on Day 2).

If the subject is no longer hospitalized at day 28, a clinical assessment will be made by an in-person or phone visit; otherwise, it would be recorded as missing data.

6 Assessment of Safety

6.1 Safety Parameters

Safety parameters will be assessed as follows:

I. Physical Examination:

The PI will conduct a thorough physical examination during screening. The assessment will be recorded in the appropriate CRF.

II. Clinical Laboratory Evaluations:

The following tests will be conducted: WBC, differential, Hgb, PLT, creatinine, glucose, total bilirubin, AST, ALT and coagulation PT.

III. Adverse Events:

Safety will be assessed by summarizing the incidence and type of Adverse Events in a CRF form.

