enrolled and treated with GT0918 since 9/6/2017 as defined in protocol at five dose levels: 100 mg (n = 3), 200 mg (n = 4), 300 mg (n = 4), 400 mg (n = 4) and 500 mg (n = 3) (as to 7/2/2019). All pts progressed more than two lines of therapies with 83.3% (15/18) pts were treated \geq 3rd lines. Out of 6 confirmed AR positive pts, two (33.3%) at 300 mg cohort had finished 17 and 19 cycles individually and continue treatment (as 7/2/19). No DLT was observed and MTD has not been reached. GT0918 related adverse events (AEs) were grade 1 or 2 as per CTCAE v4.03, including fatigue, hypertriglyceridemia, anemia, hypercholesterolemia, increased LDL, nausea, loss of appetite, increased ALT, increase of weight loss, constipation and thrombocytopenia. PK profile analysis showed that in the single-dose study, GT0918 showed a fast absorption profile. In the multiple-dose study, the steady-state serum concentration level of GT0918 and its main metabolite were attained at 21 days. Conclusions: Proxalutamide (GT0918) administrated orally once a day is well tolerated in late-stage pts. No DLT has occurred at maximum dose 500 mg. Pts with AR positive biomarker could have better clinical outcomes with GT0918 treatment. GT0918 and its main metabolite exhibited a nonlinear pharmacokinetic profile over the dose range from 100mg to 500 mg. An expanded/phase Ib in AR positive mBC pts has launched in China to evaluate the anti-tumor activity and safety of GT0918. 200 mg and 300 mg were selected for dose expansion.

Drug Interactions

Inhibition Potential Assessment of Proxalutamide on Cytochrome P450 Enzymes in Pooled Human Liver Microsomes

The inhibition of human liver CYPs: CYP1A2, CYP2C9, CYP2C19, CYP2D6, CYP2E1 and CYP3A4/5, was assessed with Proxalutamide at concentrations of 0.2, 0.8, 2, 10, 50, 100 and 200 μ M. The metabolite formation from CYP catalyzed probe substrate metabolism was analyzed with LC-MS/MS. The results showed that Proxalutamide showed no significant inhibition on CYP1A2 and CYP2E1, weak inhibition on CYP2D6, CYP2C9, CYP2C19 and CYP3A (midazolam), but marked inhibition on CYP3A4 (testosterone).

The results indicate that there is an inhibitory effect of Proxalutamide on CYP3A4 in vitro and the corresponding in vivo drug interaction potential needs to be further investigated.

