6.2 Method and Timing

The assessments, as described in section 6.1, will occur as follows:

I. Physical Examination

The assessment will occur at screening. The information will be recorded in the appropriate CRF.

II. Clinical Laboratory Evaluations:

The assessment will occur upon admission to the hospital as well as at day 14. Additional laboratory tests or timing may be ordered as deemed necessary by the PI.

III. Adverse Events:

Adverse events will be assessed daily during the 28 day duration of the trial. The information will be recorded in the appropriate CRF.

The methods employed for completing assessments are described in section 6.1

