6.3.7 Time Period and Frequency for Event Assessment and Follow-Up

For this study, all Grade 3 and 4 AEs and all SAEs occurring from the time the informed consent is signed through the Day 28 (end of study) visit will be documented, recorded, and reported.

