6.3.8 Investigators Reporting of AEs

Information on all AEs should be recorded on the appropriate CRF. All clearly related signs, symptoms, and results of diagnostic procedures performed because of an AE should be grouped together and recorded as a single diagnosis. If the AE is a laboratory abnormality that is part of a clinical condition or syndrome, it should be recorded as the syndrome or diagnosis rather than the individual laboratory abnormality. Each AE will also be described in terms of duration (start and stop date), severity, association with the study product, action(s) taken, and outcome.

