6.4.3 Reporting Unanticipated Problems to Subjects

Subjects will be informed of any UPs that occur as part of their participation in this trial.

7 Statistical Plan

7.1 *Statistical Methods*

I. General Principles:

- Double-blinded, placebo controlled randomized interventional study with a two-sided type I error rate of 0.05.
- Continuous variables will be expressed as median (interquartile range [IQR]) and categorical variables will be expressed as a number
- 95% confidence intervals will be calculated for the primary outcome
- Group comparisons will be analyzed by the Wilcoxon rank sum test or χ^2 test
- The placebo arm will be used as a reference group when calculating treatment effects
- Differences between rates of clinical improvement will be calculated using unadjusted ordinal logistic regression or Cox proportional hazard models
- Statistical analyses will be conducted using XLSTAT version 2020.5.1 (Addinsoft, Inc.)

II. Statistical Hypotheses:

The primary endpoint is the distribution of clinical assessments on the COVID-19 ordinal scale at day 14. The primary outcome will be analyzed using the Wilcoxon rank sum test.

The Null Hypothesis (H_0) is that the distribution of clinical assessments on the COVID-19 ordinal scale at day 14 among hospitalized COVID-19 subjects treated with Proxalutamide is equal to the distribution of clinical assessments on the COVID-19 ordinal scale at day 14 among hospitalized COVID-19 subjects treated with the Proxalutamide placebo

The Alternative Hypothesis (H_A) is that the distribution of clinical assessments on the COVID-19 ordinal scale at day 14 among hospitalized COVID-19 subjects treated with Proxalutamide is not equal to the distribution of clinical assessments on the COVID-19 ordinal scale at day 14 among hospitalized COVID-19 subjects treated with the Proxalutamide placebo

Mathematically written as:

$$H_0: P(X > Y) = P(Y > X)$$

$$H_A: P(X > Y) \neq P(Y > X)$$

Where X and Y are randomly selected clinical assessments from the two treatment arms in the study.

III. Primary Efficacy Analysis:

- The non-parametric Wilcoxon rank sum test (Mann Whitney U) will be used to assess the primary end point.
- P-values <0.05 will be considered significant. All statistical analysis will be based on the intent-to-treat (ITT) population. All missing data will be described.

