--	--	-------------------------------------------------------------------------------------------------------------------------------------------------------------------------------------------------------------------------------------------------------------------------------------------------------------------------------------------------------------------------------------------------------------------------------------------------------------------------------------------------------------------------------------------------------------------------------------------------------------------------------------------------------------------------------------------------------------------------------------------------------------------------------------------------------------------------------------------------------------------------------------------------------------------------

3. General principles

As proposed in the final protocol	Done in the final statistical Plan	Rationale
Continuous variables will be expressed as median (interquartile range [IQR]) and categorical variables will be expressed as a number	Continuous variables were expressed as median (IQR) and categorical variables were expressed as a number and in a risk percentage.	Expression of the categorical variables only as a number is not sufficient to allow for calculation of risk ratios. Then, absolute risk ratios were calculated for primary (14-day Overall Recovery rate) and secondary outcomes (28-day recovery rate and 28-day all-cause mortality)
95% confidence intervals will be calculated for the primary outcome	95% confidence intervals will be calculated for the primary outcome, secondary outcomes and subgroup analysis.	All secondary outcomes expressed in ratios were reported along with the 95% confidence interval to allow for a better understanding of the effect sizes.
Group comparisons will be analyzed by the Wilcoxon rank sum test or χ^2 test	For all categorial effect sizes, hypothesis testing was performed with the χ^2 test, including risk ratios. 95% Confidence intervals were reported in results tables, for the primary endpoint Overall Recovery Ratio), along with the P value. For the Adverse AE table, P-values were included. Other outcomes described as median and IQR were compared with the Wilcoxon rank sum test.	The primary hypothesis testing previously stated was maintained. However, we explained in which cases the different tests were applied to increase transparency.

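### The laboratory safety tests have no planned analysis, and the protocol conflicts on whether Grade 1–2 changes reach the adverse event table, so such changes may go unreported

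*Combined protocol and SAP*

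**What the plan says.** References are to the current protocol (men and women) and to the final statistical plan that follows it.

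- **Collection.** Section 6.1 II lists "WBC, differential, Hgb, PLT, creatinine, glucose, total bilirubin, AST, ALT and coagulation PT". Section 6.2 II gives the timing: "The assessment will occur upon admission to the hospital as well as at day 14". The investigator may order further tests.
- **Safety analysis.** Section 6.1 III: "Safety will be assessed by summarizing the incidence and type of Adverse Events in a CRF form". Section 7.3 defines the safety population (at least one dose received) and attaches no laboratory method to it. Section 3 of the final plan adds one safety item: "For the Adverse AE table, P-values were included".
- **General rules.** Section 7.1 and section 3 of the final plan give median and IQR for continuous variables and numbers (later also percentages) for categorical ones, with Wilcoxon and chi-square tests. Neither ties these rules to laboratory values or defines a laboratory category.
- **AE capture.** Section 6.3.1 allows an abnormal laboratory result to count as an AE, then says that Grade 3 and 4 AEs will be captured. Section 6.3.7 covers "all Grade 3 and 4 AEs and all SAEs occurring from the time the informed consent is signed" up to Day 28. Section 6.3.8 asks for information on all AEs, with no grade limit. For a laboratory change that belongs to a wider condition it says "it should be recorded as the syndrome or diagnosis rather than the individual laboratory abnormality".
- **Prior data.** Section 1.1.2 describes the treatment-related events of Study 2 as all Grade 1, anaemia among them. For Study 5 it says "GT0918 related adverse events (AEs) were grade 1 or 2 as per CTCAE v4.03", and its list includes anaemia, raised ALT and thrombocytopenia.

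**The concern.** The trial plans to measure liver function and blood counts in both arms but to report safety only through events that an investigator records. A laboratory change reaches the report only if someone judges it to be an AE, and, on one reading of section 6.3, only if it is Grade 3 or worse or serious. The drug-related effects described in Studies 2 and 5 fall below that line.

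The route is weak in this population for a further reason. Section 6.3.1 expects many laboratory abnormalities from the underlying illness. In that setting, attributing a mild change in one patient is hard, and a randomised comparison of the values themselves is what separates drug from disease. Without it, the report could describe good laboratory tolerability at 300 mg while the comparison that would test the statement was never made.

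**Working it through.** No figure in the plan is disputed. The check is mainly a reading of passages side by side, with some arithmetic for scale.

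**1. Is there any analysis of the laboratory values?** Sections 7.1, 7.2 and 7.3 and sections 1 to 6 of the final plan contain no change from baseline, grade count, threshold or shift table for any laboratory test. The general rules would give medians with a Wilcoxon test for raw values. They would give chi-square for categories, but no category is defined. Laboratory results therefore reach the report only as AEs.

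**2. Which grades become AEs?**

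| Section | Grades named |
|---|---|
| 6.3.1 | Grade 3 and 4 captured; abnormal laboratory findings and worsening of pre-existing conditions can be AEs |
| 6.3.5 | All AEs and SAEs are graded; Grades 1 and 2 are defined |
| 6.3.7 | Grade 3 and 4, plus all SAEs |
| 6.3.8 | All AEs |

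Under 6.3.7 alone, a non-serious Grade 1–2 change need not be recorded. Under 6.3.8 it should be, if judged an AE. The sections do not settle which reading applies.

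**3. Scale.** Study 4 (section 1.1.2) gives AE counts at 300 mg in 36 men. There are 2 cohorts × 147 = 294 treated subjects (section 7.2). Expected count = 294 × x/36, and the range applies the exact 95% CI for x/36.

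| Event | x/36 | 95% CI | Expected in 294 | Range |
|---|---|---|---|---|
| AST raised | 6 (16.7%) | 6.4–32.8% | 49 | 19–96 |
| ALT raised | 4 (11.1%) | 3.1–26.1% | 33 | 9–77 |
| Anaemia | 6 (16.7%) | 6.4–32.8% | 49 | 19–96 |
| WBC decreased | 6 (16.7%) | 6.4–32.8% | 49 | 19–96 |
| Neutrophils decreased | 3 (8.3%) | 1.8–22.5% | 25 | 5–66 |
| Platelets decreased | 2 (5.6%) | 0.7–18.7% | 16 | 2–55 |

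These are not drug-caused cases: Study 4 has no placebo arm, and the table gives no grades. The share that 6.3.7 would leave out lies anywhere from 0% (all Grade 3 or worse, or serious) to 100% (all non-serious Grade 1–2).

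**4. How complete could a Day 14 comparison be?** Section 6 of the final plan assumes 39% recovered (discharged) on placebo at 14 days and 14 points more on active, so 53%. No laboratory visit is described for discharged subjects, and section 5.2 allows contact by phone. If none returned for blood tests:

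- placebo subjects without a value: 0.39 × 294 ≈ 115, leaving about 179;
- active subjects without a value: 0.53 × 294 ≈ 156, leaving about 138.

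Deaths would reduce these further.

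**5. What precision would the table have?** Take, for illustration, 11.1% in each arm rising by at least one grade. The 95% half-width of the risk difference is 1.96 × √[0.111 × 0.889 × (1/n₁ + 1/n₀)].

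- Complete data, 294 and 294: 1.96 × √(0.0987 × 0.00680) = 5.1 points.
- Only subjects still in hospital, 138 and 179: 1.96 × √(0.0987 × 0.0128) = 7.0 points.

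The table is informative in either case. In the second it compares selected subjects.

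**The case against.** The strongest reply is that the plan does not discard low-grade changes. Section 6.3.1 lets an abnormal laboratory result be an AE, 6.3.5 defines Grades 1 and 2, and 6.3.8 asks for all AEs. That stands. A reader might infer that these harms would certainly go unreported; the documents support only that they may.

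Second, the prior data are weaker than they look. Every Study 4 laboratory row used above is marked P>0.05 across doses. ALT falls with dose (16.2%, 11.4%, 11.1%) and AST is nearly flat (13.5%, 14.3%, 16.7%). Nor is all known laboratory harm low grade: Study 3 reports Grade 3 or higher anaemia in 7 of 40, which 6.3.7 would capture. This also stands, and the point rests on the grades in Studies 2 and 5. A reader might add kidney harm because creatinine is in the panel, but the prior data list no creatinine rise.

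Third, a reader might infer that a Wilcoxon test on raw values would miss a harm confined to a minority, and that a fixed threshold would find it. That depends on assumptions outside the documents. With log-normal ALT (assumed median 30, log SD 0.5), 300 per arm and a twofold rise in 11.1% of treated subjects, simulated power was about 34–37% for Wilcoxon and 24% for Fisher's test on values above 100. With a fivefold rise it was about 62–64% against over 99%. The ordering reverses, so no power argument is made here.

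The rule in 6.3.8 about recording a syndrome is conditional, and nothing shows how often it would absorb a drug effect. Day 14 values may also be incomplete, which limits the remedy but does not justify leaving the available values unanalysed.

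**Conclusion.** The point holds in a limited form. The plan collects laboratory safety data in both arms and specifies no analysis of them. Its AE sections disagree on whether Grade 1–2 changes are recorded, so liver and blood-count changes of the kind reported in Studies 2 and 5 may not appear in the results.

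The size is uncertain. At Study 4's 300 mg rates, roughly 16 to 49 treated subjects per laboratory term would have an event, with wide intervals. The fraction lost depends on the grade mix and on which section the sites followed, neither of which the documents give. The primary efficacy analysis is untouched. The change should be made because any statement on laboratory tolerability would otherwise rest on AE recording alone.

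**What to change.** 1. Reconcile sections 6.3.1, 6.3.7 and 6.3.8 so that they state the same grades for the AE table, and state in the report which rule the sites applied.
2. Add to the final plan, on the section 7.3 safety population, a shift table by arm for each 6.1 II test that has a grade in the DAIDS 2.1 table (named in 6.3.5), from admission to the scheduled Day 14 value. Give the proportion rising by at least one grade, the risk difference with 95% CI, and the number with a Day 14 value per arm. Show it beside the AE table whether or not a change was recorded as an AE.
3. Show worst post-dose grade, including investigator-ordered tests, only as a supplementary table. Note that testing frequency depends on length of stay, which treatment may affect.

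The final plan says that its changes were made while the manuscript was being written, so a table added at that stage should be labelled as such. It would still help: events never recorded cannot be recovered by rewording section 6.3, but measured values can be tabulated.

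The cost is plan wording and one or two tables from measurements already scheduled. The downsides are incomplete Day 14 values in discharged subjects, possibly unequal between arms, and a tolerability statement that may become less favourable.
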